The Chinese government reported the first cases of pneumonia of unknown origin on December 31, 2019,³ followed by a rapid increase in the Hubei province in China during the first weeks of January 2020, expanding in continental China and neighboring countries. The World Health Organization declared COVID-19 a public health emergency of international concern on January 30, 2020⁴ and a pandemic on March 11, 2020.⁵ The pandemic reached Latin America later than other continents, and the first case of COVID-19 in the region was reported in Brazil on February 26,⁶ followed by a case in Mexico on February 28, 2020 and subsequently spreading throughout the region during March 2020.

Policy responses to COVID-19 in Latin America have sought to reduce viral spread, increase the capacity of the health system response, mitigate negative consequences, and strengthen governance.⁷ Effectiveness studies of social distancing policies in China,^{8,9} India,¹⁰ European countries^{11,12}, the United States¹³ and worldwide¹⁴ have shown that these appear to be effective to reduce viral transmission.

Despite the heavy burden of the COVID-19 in Latin American countries, there have been few studies examining the effectiveness of COVID-19 policies.¹⁵⁻¹⁷ Likewise, few studies have explored variation at the local level in the effectiveness of COVID-19 policies.^{10,13,16} Inequalities in policy effectiveness can arise due to within-country differences at the local level due to their

geographical, sociodemographic, mobility patterns, and governance differences. In Latin America, high levels of poverty, urban density, household crowding, lack of safety nets, unemployment and precarious work cluster geographically and coexist with structural inequities in governance and built environments, thus creating barriers for effective compliance with preventive recommendations and for the implementation of well-functioning contact tracing and isolation mechanisms. Understanding the effectiveness of policies at the local level and exploring potential explanations for effect heterogeneity is essential to reduce the burden of the ongoing COVID-19 pandemic and inform the preparedness for future pandemics.

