In this study, we aim, first, to estimate the effectiveness of nonpharmaceutical interventions on SARS-COV2 transmission and COVID-19 mortality in Latin America; second, to examine the effect heterogeneity of transmission and mortality at the local level. Third, assuming we find evidence of moderate to substantial heterogeneity at the local level, we aim to explore potential explanations for this heterogeneity. We will use an interrupted time series method to estimate their effects in each local government, and random effects meta-analysis and meta-regression to obtain pooled effects, heterogeneity estimates and potential explanations.

Methods

Design and setting

The study is a natural experiment where we exploit the variation in the temporal and spatial implementation of policy interventions, aimed to reduce the spread and mortality of COVID-19 in Latin America. The unit of analysis are local governments, i.e. third-tier administrative levels such as municipalities, districts or cantons.

We will include all countries fulfilling the following eligibility criteria: (1) Spanish or Portuguese speaking countries in Latin America, and (2) availability of open data at the subnational level for either of the outcomes. Appendix I presents the eligible countries, the exclusion criteria and the sources of data for each excluded country. To date, eligible countries are Argentina, Brazil, Chile, Colombia, Costa Rica, Guatemala, Mexico, Paraguay, and Peru. These countries represent 80.9%

of the population in Latin America, and the vast majority of SARS-CoV-2 cases and COVID-19 deaths.

Interventions

We will examine the impact of several interventions to tackle the COVID-19 pandemic. These interventions include (i) policies aimed at reducing viral transmission, (ii) policies aimed at increasing the capacity of the health system's response, and (iii) policies aimed at mitigating the negative consequences of the epidemic and potential adverse effects of interventions. We will use the PoliMap taxonomy to categorise the examined policies.¹⁸ Table 1 describes the policy interventions in each policy domain included in the study.

Table 1. Policy interventions included in the study

Domain	Policy interventions

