The first model at the local level does not include covariates (see below). The second model (i.e. the meta-analysis), we will examine the change in heterogeneity after adjusting for several covariates at the local level. Local level covariates include projected population size in 2020, demographic density, age-structure of the population, household density and socioeconomic status. We will use data from official sources of information, primarily the latest national population census in each included country.

Statistical analysis

The Statistical Analysis Plan provides details on the modelling assumptions. We will use an interrupted time series design, where each local government acts as its own control.^{20,21} The main

strength of this design is its capacity to distinguish the effect of the intervention from secular change.²² We will use a Poisson regression to model the count data (for both outcomes) and accounting for overdispersion and secular trends.²³ A full discussion on potential biases and violations of assumptions can be found in the Statistical Analysis Plan.

In a second stage, we will use random effects meta analysis to pool the effect estimates for each intervention or combination of interventions. This analysis informs whether any implemented intervention was effective to reduce COVID-19 cases and deaths and the degree of heterogeneity between the effects at the local level. If we observe high levels of heterogeneity (defined as higher than 50%), we will also use standard meta-regression techniques to assess whether local level determinants (see *Covariates*) can explain the observed heterogeneity.

We will build the models and test the analytical strategy using publicly available data on COVID-19 cases and deaths from Finland and Sweden from January 1 to March 31.

References

2. United Nations Department of Economic and Social Affairs. World Social Report 2020: Inequality in a rapidly changing world. New York, United States: United Nations; 2020.
3. World Health Organization. Report of the WHO-China Joint Mission on Coronavirus Disease 2019 (COVID-19)2020. <https://www.who.int/docs/default-source/coronaviruse/who-china-joint-mission-on-covid-19-final-report.pdf> (accessed March 26, 2020).

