## Introduction

The COVID-19 pandemic is evolving quickly globally. By January 22, 2021, there were more than 112 million reported cases and more than 2.6 million deaths worldwide. Latin America is one of the worst-hit regions and accounts for 20.3% of the SARS-COV2 cases and 30% of the global deaths, despite having only 8% of the global population. The effectiveness of policies to reduce the spread of COVID-19 has been analyzed in several empirical studies. Nevertheless, few of these studies have included countries in Latin America or examined the effect heterogeneity and potential explanations for it. In this study we aim, first, to estimate the effectiveness of nonpharmaceutical interventions on SARS-COV2 transmission and COVID-19 mortality in Latin America; second, to examine the effect heterogeneity of transmission and mortality at the local level. Third, assuming we find evidence of moderate to substantial heterogeneity at the local level, we aim to explore potential explanations for this heterogeneity.

This Statistical Analysis Plan (SAP) provides an in-depth description of the statistical methods and definitions for the study analysis. More information on the rationale and data sources can be found in the Study Protocol.

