### *Timing of analyses and outcome assessments*

We will use data from the date of the first case in each country until December 31, 2020. We will use publicly available daily data for all outcomes. We will use the enforcement date on data on interventions collected from PoliMap ([www.polimap.org](http://www.polimap.org)).

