#### *Outcome definitions*

The first outcome will be the 7-day moving average of daily confirmed cases of COVID-19/SARS-CoV-2. The second outcome is the time-varying reproductive number between the current and previous period. The third outcome is the 7-day moving average of the daily number of deaths by COVID-19 in Latin American subnational regions. For the statistical modelling, these averages will be rounded to the nearest integer. We will consider a 7-day lag as the primary lag. We will use the definition of COVID-19 case and death which is valid at any given time in each country.

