Assumption 2. We will explicitly incorporate co-occurring interventions in a seven-day period as a combination of interventions. We will also adjust for changes in the case definition of COVID-19 cases and deaths for each of the respective outcomes. We will report in the Supplementary Appendix the exact dates considered in the analysis for each country/subnational unit and the interventions included in each intervention period.

Assumption 3. We will introduce flexible spline functions to account for seasonality and long-term trends. We will add a scale parameter, which will be the Pearson statistic divided by the residual degrees of freedom, to account for potential overdispersion (a violation of the Poisson regression assumption). We will test for autocorrelation using the Durbin-Watson tests and visual plots of the autocorrelation function and partial autocorrelation function. If there is evidence of autocorrelation, we will use the Newey-West method to obtain adjusted standard errors.

Therefore, in the final analysis, we will use Poisson regression to model the count data.. The final model is an extension of the regression described in equation 1 with the specifications described above. The model will include each of the interventions (either as single interventions or combinations of), denoted  $j = 1, \dots, J$ . This method allows estimating simultaneously the effect of several interventions. We will consider interventions implemented within a 7-day period as a combination of interventions, following previous studies. This means that the maximum number of combinations of interventions is 52,  $t = 1, \dots, 52$ . We will estimate the effect of the interventions separately when interventions are separated by at least seven consecutive days and for a maximum period of 30 days. The primary analysis will include a 7-day lag to account for the delay in the intervention to be effective, considering the incubation period of SARS-COV2.

$$(5) \ln(Y_t) = \beta_0 + \beta_{1j}time_{tj} + \beta_{2j}post_{tj} + \beta_{3j}timepost_{tj} + \mu_t$$

This model will be run at the municipal level and, therefore, we expect to run 10,000 regressions multiplied by the number of combinations of interventions at each municipal level. Coefficient  $\beta_{3j}$  is the coefficient of interest and represents the change in slope after the intervention  $j$  at period  $t$ .

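### Rounding the 7-day averages to whole numbers stores a week with 1 to 3 events as zero and distorts the slope change β3 in municipalities where counts are sparse and trending

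*SAP*

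**What the plan says.** Two of the three primary outcomes are 7-day moving averages, one of cases and one of deaths. The SAP (Outcome definitions) and the Protocol (Outcomes) both add: "For the statistical modelling, these averages will be rounded to the nearest integer". I read this as covering cases and deaths but not the reproductive number, which is not defined as an average.

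The Protocol (Statistical analysis) then states: "We will use a Poisson regression to model the count data (for both outcomes) and accounting for overdispersion and secular trends". The SAP (Analysis methods) fits this model separately in each third-tier unit, with the slope change β3 on the log scale as the target. It adds a Pearson scale parameter for overdispersion, and Newey-West standard errors if autocorrelation is found. The β3 estimates are pooled by random-effects meta-analysis. If I² exceeds 50%, they are regressed on local covariates that include population size and density.

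The sensitivity analyses cover lag, anticipation, placebo dates and, for cases and R, under-ascertainment. None uses unrounded data. Neither document gives a reason for rounding, a minimum count per municipality, or a rule for series that are zero throughout.

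**The concern.** Rounding an average of small counts works as a threshold. Below half an event per day the series reads 0; just above, it reads 1. A log-link model estimates proportional change, and a threshold does not preserve proportional change: a slow rise across it looks steep, and so does a slow fall. A steady rise with no policy effect can appear to bend at an arbitrary date.

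β3 is the quantity that is pooled, so any distortion enters the main result directly. The distortion also depends on the count level. That matters for the aims on local heterogeneity and its explanation, because count level is likely to follow population size, a planned covariate. A difference between small and large municipalities could then come partly from how the outcome is stored.

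**Working it through.** There is no stated figure to reproduce: the documents give no municipal event rate.

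**1. The rounding rule.** Totals of 1, 2 and 3 give averages of 0.14, 0.29 and 0.43, all stored as 0. Totals of 4 to 10 give 0.57 to 1.43, all stored as 1.

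**2. A mean rate from the documents' own totals.**
- Deaths: "there were more than 112 million reported cases and more than 2.6 million deaths worldwide" and "Latin America is one of the worst-hit regions and accounts for 20.3% of the SARS-COV2 cases and 30% of the global deaths" (SAP, Introduction): 2.6 million × 0.30 = 780,000.
- Share in the eligible countries: "These countries represent 80.9" per cent of the population (Protocol, Design and setting). I take 80.9% to 100% of the deaths.
- Units: "we expect to run 10,000 regressions multiplied by the number of combinations of interventions at each municipal level" (SAP, Analysis methods). I assume 10,000 municipalities from this.
- Days: "the first case of COVID-19 in the region was reported in Brazil on February 26" (Protocol, introductory text) and "We will use data from the date of the first case in each country until December 31, 2020" (SAP, Timing). 26 February to 31 December 2020 is 310 days.

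780,000 / (10,000 × 310) = 0.252 deaths per day; × 0.809 = 0.204. With half as many units: 0.41 to 0.50. The same steps for cases give 112 million × 0.203 / (10,000 × 310) = 7.3 per day; × 0.809 = 5.9.

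**3. Share of death-containing windows stored as 0.** With S the 7-day total, the share is P(1 ≤ S ≤ 3) / P(S ≥ 1).

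At 0.252/day the mean of S is 1.76. Under Poisson variation P(0) = 0.172 and P(1) + P(2) + P(3) = 0.303 + 0.267 + 0.157 = 0.726, so the share is 0.726 / 0.828 = 88%. At 0.204/day (mean 1.42) it is 0.703 / 0.760 = 93%. In the other rows the dispersion k and the spread are assumptions.

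| Setting | Share stored as 0 |
|---|---|
| Single rate 0.20–0.25/day, Poisson | 88–93% |
| Same, negative binomial k = 1–2 | 74–85% |
| Same, k = 0.3–0.5 | 63–73% |
| Municipal means lognormal (log SD 1–2) around 0.20–0.25/day; Poisson or k = 1–2 | 71–81% |
| Single rate 0.41–0.50/day, Poisson | 52–66% |

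In the lognormal row, the zeroed windows hold about 34–53% of deaths (log SD 1) or 18–25% (log SD 2).

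**4. Effect on β3 (illustrative, because the slopes are assumed).** Take 30 days before and 30 after the intervention, daily means proportional to exp(b·t + c·t₊), scaled to the stated average rate. Here t is the day counted from the intervention, t₊ is t after the intervention and 0 before it, b is the prior slope and c the true change. Replace each day by the expected rounded value of S/7, with S Poisson or negative binomial (k = 1–2) and mean 7 times the daily mean. Fit the segmented Poisson model with level and slope change. This is a large-sample limit, not the behaviour of one 60-day series. Splines, the 7-day lag, simultaneous interventions and case-definition terms are left out.

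| Truth | Average rate | Fitted β3 |
|---|---|---|
| +0.03 then −0.02 (change −0.05) | 0.20–0.25/day | inflated 1.6–2.9 times |
| Steady +0.03, change 0 | 0.20–0.25/day | −0.019 to −0.031 |
| Steady +0.03, change 0 | 2/day | −0.001 to +0.002 |
| Steady +0.05, change 0 | 2/day | −0.006 to −0.009 |

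A flat series leaves β3 at 0 in expectation. How fast the distortion fades with higher counts therefore depends on the slope.

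**5. Why rounding is not needed.** A Poisson model with a Pearson scale is quasi-Poisson, which does not require integers. If integers are wanted, 7 times the average is the 7-day total. The factor 7 adds ln 7 to the intercept and leaves every slope coefficient unchanged.

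**The case against.** The strongest reply is that the striking figures describe a municipality at the mean, which few are. This stands in part. The 88–93% holds for one rate under Poisson variation, and spread, stronger overdispersion or fewer units lower it as tabulated. The rate itself is rough. The death total is dated 22 January 2021, after the data end, which pushes it up. Starting every country at Brazil's first case pushes it down, because each country's series starts at its own first case.

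A second reply is that the β3 figures rest on assumed slopes and a simplified model. That is correct, and they show direction and plausible size only.

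A third is that the placebo tests are a safeguard. They could help: a placebo date on a rounded steady rise might show a false bend. They use the same rounded series, however, so they would neither isolate rounding nor remove its effect.

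A reader might also infer that the pooled effect must be materially biased. The documents do not support that. The pooled result depends on the weights and on which sparse units are kept, and the SAP gives no rule for the latter. In simulations with a true change of 0, requiring at least 3 non-zero days per segment gave a pooled false change of −0.010 to −0.051; requiring 6 gave −0.029 to +0.001. Neither rule is in the plan. Nor should rounding be blamed for a high I², which in the first set of simulations was 0.82–0.87 rounded and 0.83–0.87 unrounded.

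Finally, a reader might take this as a problem for deaths only. A case series at 5.9–7.3 per day is little affected, but with log SD 2 about 37–41% of municipalities would average under 0.5 cases per day, where the same threshold applies.

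**Conclusion.** The point holds as a defect of a stated rule. The storage effect is certain: totals of 1 to 3 become 0. On the documents' totals, and assuming about 10,000 units, most windows that contain a death would be zeroed in a typical municipality. The share runs from just over half to above 90%, depending on rate, dispersion and spread.

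β3 is distorted where counts are both sparse and trending, and with no true effect during a rise the error is in the protective direction. The distortion shrinks as counts rise, at a pace set by the slope. The size of the pooled bias cannot be derived from the documents and may be small if large municipalities dominate the weights. The exposure of the heterogeneity aim, and of the meta-regression on population size and density, remains in either case, because the distortion varies with count level. No planned analysis removes it, and the rounding brings no benefit to set against it.

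**What to change.** Delete the rounding sentence in the Protocol (Outcomes) and the SAP (Outcome definitions). For cases and deaths alike, state instead:

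> The 7-day moving average is modelled unrounded with a quasi-Poisson model (log link, Pearson scale) or, equivalently, the integer 7-day total is modelled; Newey-West standard errors are kept.

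Add to the SAP's sensitivity analyses a fit to raw daily deaths with a day-of-week term. Report how many municipalities have a β3 that cannot be estimated.

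The cost is one sentence in each document, the family argument in the planned *glm* call, one extra sensitivity analysis and one reported count. The outcomes remain 7-day averages. The remedy is partial: unrounded overlapping averages keep some small-count bias (1.08 to 1.56 times the true change when pooled, in simulations under assumed settings with the 3-day rule). Raw daily counts came closer but were usable in fewer municipalities, so they suit a sensitivity analysis better than a replacement.

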#### *Analysis methods*

The primary analysis will use interrupted time series (ITS) for each subnational unit to examine the causal effect of COVID-19 policies on primary outcomes. Interrupted time series is a widely used tool in causal inference that allows comparing trends before and after the introduction of an intervention. The counterfactual outcome is the projection of the trend in the period before the introduction of the intervention into the time period was introduced. The unit of analysis in this study is days, starting from the date of the first case.

The standard model for an ITS regression is as follows

$$(1) Y_t = \beta_0 + \beta_1 time_t + \beta_2 post_t + \beta_3 timepost_t + \beta'_4 X + \mu_t$$

where  $time_t$  is a variable which equals one at the first time point  $t$  and increases by one after each subsequent time point;  $post_t$  is a dummy variable that equals to zero prior to the introduction of the intervention ( $p$ ) and equals one for every time point thereafter;  $timepost_t$  is a variable that equals to zero until time  $p-1$ , and increases by one for each subsequent time point; and  $X$  is a vector of covariates. Coefficient  $\beta_3$  is the coefficient of interest and represents the change in slope after time  $p$ .

The validity of the ITS rests on three assumptions. Assumption 1 states that the expectation of the pre-intervention level and trends would be the same irrespective of whether the sample received the treatment. Assumption 2 states that in the absence of treatment, the outcome of interest would remain unchanged in the post-intervention period. Assumption 3 states that the time trends in the pre and post periods can be expressed as a linear combination of parameters.

Using the potential outcomes framework, the estimated effect of a policy at time  $p$  could be defined as

$$(2) \Delta_t = Y_t(1) - Y_t(0)$$

These difference could also be expressed in terms of two equations

$$(3) Y_t(1) = \alpha_0 + \alpha_1 time_t + \alpha_2 post_t + \alpha_3 timepost_t + \varepsilon_t$$

$$(4) Y_t(0) = \theta_0 + \theta_1 time_t + \theta_2 post_t + \theta_3 timepost_t + \nu_t$$

where  $Y_t(1)$  is the sequence of outcomes if we treat the unit at time  $p$  and  $Y_t(0)$  the sequence of outcomes in the absence of treatment. Assumption 1 implies no anticipation of treatment, i.e.  $Y_t(1) = Y_t(0)$  for all  $p \leq t_0$ . In other words,  $\alpha_0 = \theta_0$  and  $\alpha_1 = \theta_1$ . Assumption 2 implies that  $\theta_2$  and  $\theta_3$  are equal to zero.

Violations of assumption 1 include anticipation effects when the subjects of the policy can anticipate its initiation and change their behaviour. In the case of the COVID-19 pandemic, the population might, for example, be more likely to adhere to social distancing recommendations during the discussion of a lockdown or take preventive actions when the incidence of cases increases, even before restrictions such as lockdowns are implemented. Violations of assumption 2 include concurrent changes due to history (other concurrent policy, program or societal changes), selection (changes in the composition of the sample at time  $p$ ), instrumentation (changes in the way the outcome is measured) and mis-specification of the functional form of the time trend (in a classical ITS, time is assumed to be a simple linear term). Violations of assumption 3 can occur due to misspecification of the functional form, including failing to account for a delay of the policy to take effect or failing to account for autocorrelation (which can lead to artificially low standard errors). In an epidemic process, cases over time follow a non-linear trajectory (often an exponential, Gompertz or other complex functional forms). Assuming a linear time trend can lead to incorrect counterfactuals and biased effect estimates.

We will examine and handle potential violations to assumptions in the following way:

Assumption 1. We will assess the existence of anticipation effects by visual exploration and examination of the slope prior to the intervention. If there is evidence of potential anticipation effects, we will use a “quasi-myopic” sensitivity analysis, i.e. an analysis that excludes a period of time where anticipation is expected to have happened from the analyses.

Assumption 2. We will explicitly incorporate co-occurring interventions in a seven-day period as a combination of interventions. We will also adjust for changes in the case definition of COVID-19 cases and deaths for each of the respective outcomes. We will report in the Supplementary Appendix the exact dates considered in the analysis for each country/subnational unit and the interventions included in each intervention period.

Assumption 3. We will introduce flexible spline functions to account for seasonality and long-term trends. We will add a scale parameter, which will be the Pearson statistic divided by the residual degrees of freedom, to account for potential overdispersion (a violation of the Poisson regression assumption). We will test for autocorrelation using the Durbin-Watson tests and visual plots of the autocorrelation function and partial autocorrelation function. If there is evidence of autocorrelation, we will use the Newey-West method to obtain adjusted standard errors.

Therefore, in the final analysis, we will use Poisson regression to model the count data.. The final model is an extension of the regression described in equation 1 with the specifications described above. The model will include each of the interventions (either as single interventions or combinations of), denoted  $j = 1, \dots, J$ . This method allows estimating simultaneously the effect of several interventions. We will consider interventions implemented within a 7-day period as a combination of interventions, following previous studies. This means that the maximum number of combinations of interventions is 52,  $t = 1, \dots, 52$ . We will estimate the effect of the interventions separately when interventions are separated by at least seven consecutive days and for a maximum period of 30 days. The primary analysis will include a 7-day lag to account for the delay in the intervention to be effective, considering the incubation period of SARS-COV2.

$$(5) \ln(Y_t) = \beta_0 + \beta_{1j}time_{tj} + \beta_{2j}post_{tj} + \beta_{3j}timepost_{tj} + \mu_t$$

This model will be run at the municipal level and, therefore, we expect to run 10,000 regressions multiplied by the number of combinations of interventions at each municipal level. Coefficient  $\beta_{3j}$  is the coefficient of interest and represents the change in slope after the intervention  $j$  at period  $t$ .

In coefficient of interest at a second stage, we will pool the effects for each intervention -or combination of interventions- (i.e. the coefficient of interest  $\beta_{3j}$  from the local level regression) using a random-effects meta-analysis. This meta-analysis will provide information to obtain a pooled effect estimate and a measure of heterogeneity. We will use the  $I^2$  as a measure of heterogeneity.

If the heterogeneity is moderate or high ( $I^2$  higher than 50%), we will carry out a meta-regression to assess whether subnational level determinants can explain the observed heterogeneity. We will analyse the following covariates: (i) Population size, (ii) Population density, (iii) Proportion of population over 60 years old, as a proxy for age structure of the population, (iv) Household density, and (iv) Proportion of population with basic education, as a proxy of socioeconomic status.

The meta-regression has the effect size  $\widehat{\theta}_k$  of a first-stage regression  $k$  as the outcome, covariates  $x_{ik}$ , a fixed effect  $\rho_1 S_a$  for the second-tier level  $a$  (i.e. State or Region) and a random-effect  $\delta_2 N_b$  for the national level  $b$  and a fixed effect  $\rho_2 Y$  for the time of the year (quarterly periods)(equation 6). The equation includes two types of independent errors, where  $\varepsilon_k$  is the sampling error of the effect size and  $\varsigma_k$  is the random-effect error term.

$$(6) \theta_k = \gamma_1 x_{1k} + \dots + \gamma_n x_{nk} + \rho_1 S_a + \delta_2 N_b + \rho_2 Y + \varepsilon_k + \varsigma_k$$

These controls for higher levels of administration and time of the year will allow us to control for constant characteristics at the subnational and national level, as well as changes in the effectiveness throughout the pandemic.

We will carry out the following sensitivity analyses: (1) comparison of effect estimates using a 5-day and 10-day lag; (2) quasi-myopic analyses to control for anticipatory effects (if there is evidence of), and (3) placebo tests evaluating changes at times when no policy was implemented. In the analyses for the number of cases and time-varying R, we will run additional sensitivity analyses estimating the number of SARS-CoV-2 cases corrected by under-ascertainment derived from mortality statistics.

